5.1. Numbers of Participants

5.1.1. Number to be screened: $n \le 80$

5.1.2. Number to be enrolled: Our target sample size is N = 40.20 participants will be enrolled in the BA + tACS condition and 20 will be enrolled in the BA + active sham condition. Conservatively, we may enroll up to 80 participants, but a potentially substantially high number of people may not meet criteria for MDD as assessed by the MINI at the baseline visit.

5.2. Eligibility Criteria

Eligibility will be determined based on inclusion and exclusion criteria, defined below.

5.2.1. Inclusion Criteria

In order to be eligible to participate in this study, an individual must meet all of the following criteria:

- Between the ages of 18 and 65
- Able to provide informed consent
- Willing to comply with all study procedures and be available for the duration of the study
- Speak and understand English
- DSM-5 diagnosis of major depressive disorder (MDD) as assessed by the MINI

5.2.1. Exclusion Criteria

Any individual who meets one or more of the following criteria will be excluded from participation:

- Participants must not have active suicide intent as determined by the Columbia Suicide Severity Rating Scale (C-SSRS). Active suicide intent will be captured in responses to items 4 and/or 5 on the C-SSRS.
- Participants must not meet criteria for current severe substance use disorder, anorexia nervosa, or active psychosis as captured by the MINI.
- Participants may not currently be in psychotherapy and have not received any other psychotherapy and/or stimulation (ECT, TMS) within the last 4 weeks.
- Any participants taking psychotropic medication must be on a stable dose for at least 4 weeks with no planned dose changes within the next 4 weeks.
- (for female participants) Participants must not be pregnant or breastfeeding.
- Participants may not have any medical or neurological illness for which symptom presentation or treatment could interfere with study participation
- Participants may not have undergone prior brain surgery
- Participants may not have any brain devices/implants, including cochlear implants and aneurysm clips
- Participants may not have had brain injury or concussion within the last three months
- Participants may not have a history of brain injury requiring current treatment

5.3. Enrollment/Selection Strategies

5.3.1. Prospective Recruitment -or- Retrospective Selection

To aid in recruitment, we will advertise the study directly to the public on websites such as ClinicalTrials.gov, frohlichlab.org and Carolinaneurostimulation.org. We will have contact information and a summary of the clinical trial

Protocol Number <#>

posted on the [name] Lab social media pages. We may also be launching a social media ad to identify potential patients. This ad will also use a pre-screening survey via REDCap to help identify participants. We will also be using the UNC Mass email listserv and an IRB-approved registry. All patient identifiers will be stored in REDCap until recruitment is over. When recruitment is over, all patients who do not consent or are not eligible for participation in the study will have their responses permanently deleted in REDCap.

5.3.2. Screen Failures

In the design of this study, initial phone screening procedures should identify the majority of participants who could potentially become screen failures if consented to participate in the clinical trial. However, the phone screening process does not necessarily account for all exclusion criteria. In the case that a participant meets initial criteria, there is still a chance that the first interview reveals that they do not meet study criteria. The study personnel completing the interviewing process will clearly explain why the participant does not meet criteria. However, in the case that a participant does not qualify based on suicide risk, procedures will be followed to ensure participant safety.

At the first session and after obtaining participant informed consent, the C-SSRS will be administered, which contains questions related to suicidal thoughts/actions. If someone indicates intent based on the C-SSRS, their participation in the study will be immediately stopped and [name] (Co-I, responsible for participant safety) will be contacted for acute assessment. In the case that the person does not see anyone for their depression, [name] will provide the participant with resources for seeking psychological care.

Assessment may include facilitating contact of the participant with their psychiatrist/primary care physician to establish a plan for safety, continued care, and follow-up. If the participant does not have an established provider, [name] will assist the participant in establishing care. If at any point in the assessment, the participant is deemed to be an imminent risk of harm to self or others, study personnel will contact the Emergency Department for further care.

5.4. Strategies for Retention

Retention will be primarily achieved by the short duration of participation. Namely, the study includes a single intervention session, preceded by and followed by additional study visits. Participants will be paid \$45 for participation in the initial study visit, \$15 for the intervention/stimulation visit, and \$30 for the two-week follow up visit. Participants will also be sent questionnaires to complete virtually 4 weeks after the intervention visit, and they will be paid \$10 for completion of these questionnaires. Total payment for completion of all visits in the study totals \$100. This virtual visit will reduce burden on participants to travel for an additional study visit. The participant will receive payment at the end of each session on a payment card that can be loaded. The research staff will also give each participant a reminder call or email for upcoming sessions. Each research staff member will be available for the participants to contact via email or phone.

5.5. Matching and Stratification

N/A

5.6. Randomization and Concealment

[name], a [name] Lab member, will oversee the randomization of 40 6-digit codes, which will be used by the experimenters. These codes are directly linked to which treatment participants receive (sham/placebo or 10 Hz tACS at 1 mA) and will be entered into the MATLAB script. In addition, 10 codes will be generated in the event that a participant is randomized but discontinues the study. Data will be collected until we reach out target of 40 participants, but there will be no bias towards completion for the different arms (in the unlikely event that one of the arms has more dropout than the others). The assignment of each participant cannot be determined by looking at the codes (e.g., codes are not sequential, code assignment is not based on "odd" or "even" numbers). Thus, the study is both randomized and concealed by virtue of using random numbers generated by a computer. [name] has no other responsibility in the study other than providing these randomized codes. If [name] leaves the [name] Lab, another equivalent researcher who does not work with human participants will perform this task.

5.7. Blinding

This study is designed to be double-blind. This means that the participant and the researchers are unaware of each participant's assignment until the completion of all data collection. This is accomplished using the randomization codes described above. Furthermore, this study utilizes an active sham stimulation. This means that the active sham condition includes some stimulation, mimicking the skin sensations associated with tACS. In our previously concluded trial, participants in the delta-beta tACS and active sham groups responded similarly to the blinding questionnaire, indicating that our active sham stimulation successfully blinded the participants.

6. Treatment Design: Procedures

Description All participants will receive the behavioral activation (BA) psychotherapy intervention. This intervention occurs in a single 90-minute session. Participants are randomized to receive either an active stimulation or sham stimulation using transcranial alternating current stimulation (tACS).

Acquisition The DC-STIMULATOR MC is a CE-certified medical device is owned and operated by the Carolina Center for Neurostimulation / [name] lab.

Concomitant Therapies Participants will be ineligible to participate in this study if they are currently receiving another form of psychotherapy, TMS, and/or ECT. Individuals prescribed psychiatric medication must be on a stable dose (>4 weeks). Concomitant medications will be logged at the first session. Participants will be requested to include the dosing for these therapies (i.e., how often per day, how much in each pill, how many pills) as well as when they were first prescribed the medication.

7. Schedule of Activities and Procedures

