2.2. Scientific Rationale

This study is a randomized, sham-controlled interventional parallel-arm clinical trial. All participants will receive the same single-session BA intervention. Concurrent with the goal-directed phase of the BA intervention, participants will receive either delta-beta tACS or an active sham stimulation. All researchers involved in data collection and the participants receiving stimulation will be blind to the stimulation condition to reduce bias in the data collection process, i.e., double-blinding. A previous study in the lab found that depressed participants demonstrated reduced delta-beta coupling (Riddle et al., Cerebral Cortex 2022), and a study currently ongoing is testing the impact of delta-beta stimulation on performance during a reward-related decision-making task (NCT05084924). Moreover, another previous study recorded EEG during the S-EEfRT in patients with MDD. This study found that participants with MDD demonstrated reduced goal-directed behavior and reduced delta-beta coupling. This preliminary data provides strong evidence that stimulation delivered in a delta-beta pattern should be beneficial to reward-related behavioral outcomes that are the focus of BA. The proposed study will build on these findings to determine whether a BA intervention combined with targeted stimulation may lead to improved treatment outcomes in reward-related constructs.

3. Specific Aims

3.1. Aim 1

(PRIMARY) Evaluate the effects of delta-beta transcranial alternating current stimulation (tACS) on depression symptom severity from pre- to post-treatment.

3.2. Aim 2

(SECONDARY) Examine changes in goal-directed behavior during a reward-based decision-making task from pre- to post-treatment.

3.3. Aim 3

(SECONDARY) Investigate changes in delta-beta coupling during a reward-based decision-making task from pre- to post-treatment.

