8.1. Strategies that Apply to all the Aims

All testing described below assumes a significance threshold of p = 0.05. Analyses will be deemed to be statistically significant if the p-value is less than this threshold. An analysis that does not exceed this threshold will be considered inconclusive.

There may be additional covariates included in the analysis. Data will be assessed for normality and, if deemed necessary, corrective procedures will be applied (e.g., log normalization). Based on our previous dataset, we expect that the variables used here will be approximately Gaussian. However, if the distribution of a variable displays a skewed tail and a test for normality fails, then it is justified to use a corrective procedure. This correction will be applied upon consideration of the variables themselves, and not based on the result of the intended analysis.

Human studies are prone to drop-out, missing data, and interval-censored values. The reasons for drop outs, missing / censored data values, and protocol departures will be documented in the database. Best practices for dealing with incomplete data will depend on the documented causes of those occurrences.

The analysis plans will include outcome-dependent exploratory analyses to generate new hypotheses.

To help ensure replicability of the research, the analysis plans will be reviewed and finalized prior to collection of data (*a priori*). For each specific aim, the analysis plans specify detailed steps for obtaining estimates of the population parameters of interest (e.g., treatment effects) and for making inferences.

- Human studies are prone to drop-out, missing data, and interval-censored values. The reasons for drop-outs, missing / censored data values, and protocol departures will be documented in the database. Best practices for dealing with incomplete data will depend on the documented causes of those occurrences. In the analysis plans established a priori, the strategies for coping with incomplete data will be based on anticipated causes. Alternative methods for dealing with incomplete data will play important roles in the sensitivity analyses.
- All hypothesis tests yielding large p-values will be reported as being inconclusive. For all sample sizes, all hypothesis test procedures are (by design) incapable of establishing that the null hypothesis is true.

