8.3. Aim-Specific Plans

Plans for Aim 1 (PRIMARY).

Treatment response will be calculated as the depression (HDRS) scores from pre- to post-treatment. A two-way analysis of variance (ANOVA) will be performed using within-participant factor of time (before or after treatment), between-participant factor stimulation type (delta-beta tACS, active-sham), and the interaction between time and stimulation type. We hypothesize to find an interaction between time and stimulation type. Post hoc differences will be investigated. We hypothesize that the predicted interaction will be driven by a decrease in depressive symptoms for delta-beta tACS compared to the active-sham. Sensitivity analyses will be conducted to evaluate the specificity of these effects: a similar analysis with anxiety symptoms as the dependent variable and we do not expect that delta-beta tACS will have any effect on anxiety symptoms.

Further, we will conduct exploratory generalized linear mixed models will be conducted to examine potential confounds on treatment effect (e.g., age, sex, baseline depressive symptoms).

Plans for Aim 2 (SECONDARY).

Delta-beta phase amplitude coupling will be calculated between the phase of delta oscillations (2-3 Hz) in prefrontal electrodes (FCz and surrounding electrodes) and the amplitude of beta oscillations (15- 25 Hz) in left motor electrodes (C3 and surrounding electrodes). The instantaneous phase and amplitude of these oscillations will be calculated by averaging the signal in these two regions of interest, band-filtering the signal to the specified range, and then performing the Hilbert transform on the signal. Phase-amplitude coupling (PAC) is then calculated by creating a hybrid signal using the amplitude of beta oscillations in left motor electrodes and the phase of delta oscillations in prefrontal electrodes:

[†][1] www.consort-statement.org , [2] www.strobe-statement.org, [3] www.icmje.org

^[4] Wasserstein RL, et al. (2016), The ASA's Statement on p-Values, *The American Statistician*, 70:2, 129-133.

^[5] Wasserstein RL, et al. (2019), Moving to a World Beyond p < 0.05, *The American Statistician*, 73:sup1, 1-19.

^[6] Amrhein, et al. (2019), Scientists rise up against statistical significance, *Nature* 567, 305-307.

^[7] Editorial (2019) It's time to talk about ditching statistical significance: ... *Nature* 567, 283-283.

$$PAC = \left| \frac{\sum_{t=1}^{N} M * e^{i\theta}}{N} \right|$$

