13.7. Clinical Monitoring Plan (CMP)

The purpose of the monitoring plan is to present the approach of the Carolina Center for Neurostimulation to monitoring clinical trials. The plan facilitates compliance with good clinical practice.

- (a) The rights and well-being of human participants are protected.
- (b) The reported trial data are accurate, complete, and verifiable from source documents.
- (c) The conduct of the trial is in compliance with the currently approved protocol/amendment(s), with GCP, and with applicable regulatory requirement(s).

This section identifies key monitoring activities and specifies the data to be reviewed over the course of a clinical trial. This is a single site, investigator initiated, clinical trial so there will be no site monitoring plan in place.

The latest version of the approved IRB application for this clinical trial will be followed at all times. This responsibility falls in the hands of the trained research personnel. If at any time there is a deviation from protocol, the deviation from protocol log will be filled out. All team members will be trained on how and when to use this log. Deviations will be sent to IRB every 4-6 weeks (if necessary).

Data will be verified for completeness following every study session and all data will be entered into REDCap, a secure online database. After a participant has completed their participation (full completion through the 2-week follow-up visit or because they withdrew prior to completion), data will be rereviewed for completeness and accuracy. After all data has been collected, data will be re-reviewed by another lab member who was not involved with the data collection process.

AE and SAE are clearly defined in the Master Protocol. Documents of AE and SAE can be found in the study binder on file within [name]. It is responsibility of trained research personnel to report all events to the PI. Reporting of AEs and SAEs is described within Section 12.3.

The PI and Co-I will have read-only access to the REDCap database. This allows the PI and Co-I to view reports that provide information on any missing data on an individual participant basis, but does not allow them to add, change or input any data.

Quality Assurance and Quality Control

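### The blind may end when data collection ends, before the final data re-review, and nothing requires database lock or blinded processing before the codes are opened

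*Combined protocol and SAP*

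**What the plan says.** Section 5.7 defines the double blind by its end point: "the participant and the researchers are unaware of each participant's assignment until the completion of all data collection". Section 2.2 (Scientific Rationale) gives its scope and purpose: "All researchers involved in data collection and the participants receiving stimulation will be blind to the stimulation condition to reduce bias in the data collection". Neither section mentions a database lock, a blinded data review, or a blinded analyst or EEG processor.

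Section 13.7 (Clinical Monitoring Plan) describes three rounds of checking: after each session, after each participant finishes or withdraws, and a last one: "After all data has been collected, data will be re-reviewed by another lab member who was not involved with the data collection process". It also gives the principal investigator and co-investigator read-only database access.

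Section 8.1 leaves some choices open. On covariates: "There may be additional covariates included in the analysis". On missing data: "Best practices for dealing with incomplete data will depend on the documented causes of those occurrences". On transformation it is tighter: "This correction will be applied upon consideration of the variables themselves, and not based on the result of the intended analysis". It also says that analysis plans are to be finalised before data are collected, that missing-data strategies set in advance will rest on anticipated causes, and that alternative methods will serve as sensitivity analyses.

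Section 8.3 fixes the primary model as time, stimulation type and their interaction, and puts age, sex and baseline severity into exploratory mixed models. For delta-beta coupling it sets the bands, filtering, Hilbert transform, coupling formula and z-scoring against shifted data, starting from regional averages: "The instantaneous phase and amplitude of these oscillations will be calculated by averaging the signal in these two regions of interest".

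Section 5.6 gives the randomization codes to a lab member with no other role in the study.

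**The concern.** A blind that ends with collection protects the ratings and the recordings. It does not by itself protect what is done to them afterwards. Whoever corrects a late query, discards an EEG segment, adds a covariate or settles how to treat a missing week-2 HDRS could, under the present wording, know which arm the participant was in. Each step involves judgement, and each can shift the time-by-stimulation contrast towards the hypothesis stated in section 8.3. With 20 participants per arm, a few such decisions can matter. A reader of the eventual report would have no documented assurance that they were made blind.

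**Working it through.** No stated figure is at issue, so the check compares the text for each step: when it happens, whether it must be done blind, and what already limits it.

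| Step | Placed after collection? | Blinding required? | Existing limit |
|---|---|---|---|
| HDRS rating at baseline and 2 weeks | No, it is collection | Yes (2.2, 5.7) | Fully covered |
| Final re-review | Yes, explicitly (13.7) | Not stated | Two earlier rounds of checks; reviewer not a data collector; investigators read-only |
| EEG preprocessing and exclusions | Timing not stated | Not stated | Coupling computation fixed in 8.3 |
| Transformation | Timing not stated | Not stated | Needs a skewed tail and a failed normality test; may not rest on the result (8.1) |
| Covariates | Timing not stated | Not stated | Primary ANOVA fixed; confounders in exploratory models (8.3) |
| Missing-data method | Depends on causes as documented (8.1) | Not stated | To be set in advance from anticipated causes; alternatives as sensitivity analyses |

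**Re-review.** The earliest permitted unblinding and the start of the re-review are the same event, the end of collection. The reviewer is independent of collection but is not said to be blinded. This ordering is on the page.

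**EEG.** Section 8.3 leaves little freedom in the coupling statistic. It gives no artifact rule, no criterion for excluding epochs or recordings, no list of the electrodes neighbouring FCz and C3, no timing and no blinded processor. The exposure is by silence and affects a secondary outcome.

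**Covariates and missing data.** The primary model in 8.3 has no covariates, but 8.1 allows some to be added without naming them. A missing-data strategy is promised in advance, but none is written down. The Synopsis expects at least 30 with complete data. If exactly 30 of 40 are complete, (40 − 30)/40 = 25% are incomplete, so the missing-data choice may not be trivial.

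**Worst-case size.** A null simulation with 20 per arm and 3,000 trials per scenario used assumptions that are not in the documents: HDRS mean 20 (SD 5) before and 16 (SD 6) after, correlation 0.5, arm-independent dropout of 0, 10 or 25%. It took the smallest p over raw or log scale, four covariate sets, and complete cases or carry-forward.

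- Single raw, unadjusted, complete-case test: 4.6%, 6.1% and 5.1% at the three dropout levels. The Monte Carlo standard error near 5% is √(0.05 × 0.95/3000) = 0.4 percentage points.
- Best of all variants: 9.1%, 13.0% and 12.6%.

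Part of that figure assumes conduct that 8.1 forbids. A second null simulation (6,000 trials; HDRS 18, SD 4.5, before and 11, SD 6, after, correlation 0.4; Shapiro-Wilk at 0.05 with positive skew as an assumed gate) isolated the transformation:

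- Raw scale only: 4.8%.
- Free choice of the better of raw and log: 6.8%.
- Log only when the gate opens: 4.8%.
- Better of the two, but only when the gate opens (9% of trials): 5.0%.

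Under those assumptions, the written transformation rule removes nearly all of that component. What remains comes from covariates and missing data. The simulations measure freedom to select a result, not the effect of the unblinding date.

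**The case against.** The strongest reply is that most of this is already controlled. HDRS is rated blind. Data are checked after every session and again after each participant, both while the blind holds. The investigators cannot edit the database. The primary model is fixed, transformation may not follow the result, and alternative missing-data methods are assigned to sensitivity analyses. Section 5.7 also sets only the earliest point at which the blind may end; it does not order release of the codes before the analysis decisions.

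Much of that stands, and it limits the point to a gap in wording. A reader might infer more: that the plan schedules EEG processing and the analysis choices after unblinding, or that the trial's true error rate is 9 to 13%. The documents support neither. They give no timing for EEG processing or for the transformation and covariate decisions, and carry-forward, which the simulation uses, appears nowhere in them.

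The reply does not remove the gap. None of the safeguards requires a step to be done blind to arm. The transformation rule does not reach covariates, missing data, late corrections or EEG exclusions. Finalising a plan in advance does not close choices that the written plan leaves open.

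**Conclusion.** The point holds in limited form. The written rule lets the blind end before the last data check, and no section requires database lock or blinded processing first. The order is explicit for the re-review only; for the other steps the conclusion rests on the absence of any requirement. On the primary outcome the exposure is confined to late data corrections, covariates and missing data, with transformation largely closed by section 8.1. On the coupling outcome it lies in preprocessing and exclusions.

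The size of any bias cannot be estimated from the documents. The simulated rates are a worst case of deliberate selection under assumed inputs and should not be quoted as an expected effect. Confidence is moderate. The change is worth making because the gap is real and cheap to close. No sample size, alpha or power figure is affected.

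**What to change.** In section 5.7, replace the present end point of the blind with:

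> Assignments stay concealed until the section 13.7 re-review is complete and the database is locked; EEG preprocessing, exclusions and PACZ values are final; and any transformation, covariate and missing-data decisions are signed and dated. The code holder releases the key only then.

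State in section 2.2 that those who process EEG, review data and prepare the analysis are covered by the blind. Holding the key closes the selection route by construction, because arm comparisons cannot be computed without it.

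The cost is a protocol wording change, with the IRB review any amendment needs, and a short delay before the unblinded analysis. The independent code holder in section 5.6 already exists, so no added staff or visits are needed.
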